2.4 Schedule of Procedures Part B (same activities for Parts B1 and B2)

| Procedure | Screening | Dosing | | | | | | | | | | | | | | | Pre-Recurrence | | Post-Recurrence | End of Study ¹ |
|------------------------------------|----------------|------------------|-----|-----|-----|-----|-----|-----|-----|-----|-----|------|------|------|------|------|----------------|----------------|-----------------|---------------------------|
| | | First Visit (W0) | W 2 | W 4 | W 6 | W 8 | M 3 | M 4 | M 5 | M 6 | M 9 | M 12 | M 15 | M 18 | M 21 | M 24 | Q 3 Mos | Q 6 Mos | Q 6 Mos | |
| Baseline Documentation | | | | | | | | | | | | | | | | | | | | |
| Informed Consent | X | | | | | | | | | | | | | | | | | | | |
| Randomization | | X | | | | | | | | | | | | | | | | | | |
| Medical History | X | X | | | | | | | | | | | | | | | | | | |
| Physical Exam | X | X | | | | | X | | | X | X | X | X | X | X | X | X | | X | |
| Pathology Review | X | | | | | | | | | | | | | | | | | | | |
| BRAF mutation status ² | X | | | | | | | | | | | | | | | | | | | |
| Laboratory Studies | | | | | | | X | | | | | | | | | | | | | |
| Biomarker ³ | | X | | | | | X | | | X | X | X | X | X | X | X | X | X | X | |
| LDH | X | X | | | | | X | | | X | X | X | X | X | X | X | X | X | X ⁴ | |
| CBC and serum chemistry | X | X | X | X | X | X | X | | | X | | X | X | X | X | X | X | X | X | |
| Urinalysis | X | X | X | X | X | X | X | | | X | | X | X | X | X | X | X | X | X | |
| Pregnancy test | X | | | | | | | | | | | | | | | | | | X | |
| Serum FSH/estradiol | X | | | | | | | | | | | | | | | | | | | |
| ECG | X | | | | | | | | | | | | | | | | | | X | |
| HIV test | X | | | | | | | | | | | | | | | | | | | |
| ANA/ESR | X | | | | | | | | | X | | X | | X | | X | | | | |
| Tumor Assessments | | | | | | | | | | | | | | | | | | | | |
| Recurrence Assessment ⁵ | X ⁶ | | | | | | | | | X | | X | | X | | X | | X | | |
| Dosing | | | | | | | | | | | | | | | | | | | | |
| Seviprotimut-L or placebo | | X | X | X | X | X | X | X | X | X | X | X | X | X | X | X | | | | |
| Other Clinical Assessments | | | | | | | | | | | | | | | | | | | | |
| Survival Follow-up Contact | | | | | | | | | | | | | | | | | | X | | |
| Autoimmune Phenomena ⁷ | X | | | | | | | | | X | | X | | X | | X | | | | |
| Adverse Events | | X | X | X | X | X | X | X | X | X | X | X | X | X | X | X | X | X ⁸ | | |
| Concomitant Medications | X | X | X | X | X | X | X | X | X | X | X | X | X | X | X | X | X | X ⁹ | X | |

¹ At time of recurrence or study completion for subjects without recurrence

² BRAF tumor mutation V600E status must be either known at Screening or a tumor tissue (fresh or archived sample) must be available for testing during the Study.

³ Sera samples and PBMCs will be banked at these time points for biomarker analyses and Immune monitoring (Section 9.3.2 of the Protocol)

⁴ For subjects who have not had recurrent disease

⁵ See Section 9.3.1 of the Protocol for details

⁶ To be performed if the protocol-specified assessments have not been performed after the surgical resection, or the data are not available to the Sponsor

⁷ Include eye exam (by an ophthalmologist) and skin exam for vitiligo and rashes thereafter.

⁸ Adverse events collected through 30 days after last dose.

⁹ New cancer treatments only

2.5 Schedule of Procedures Open-Label Extension Study of Part A

| Procedure | Pre-Dosing | Dosing Period | | | | | | | | | | | | | | | Pre-Recurrence | | Post-Recurrence | End of Study ¹ |
|-----------------------------------|----------------|------------------|-----|-----|-----|-----|-----|-----|-----|-----|-----|------|------|------|------|------|----------------|-----------------|-----------------|---------------------------|
| | | First Visit (W0) | W 2 | W 4 | W 6 | W 8 | M 3 | M 4 | M 5 | M 6 | M 9 | M 12 | M 15 | M 18 | M 21 | M 24 | Q 3 Mos | Q 6 Mos | Q 6 Mos | |
| Baseline Documentation | | | | | | | | | | | | | | | | | | | | |
| Informed Consent | X | | | | | | | | | | | | | | | | | | | |
| Physical Exam | | X ² | | | | | X | | | X | X | X | X | X | X | | X | | X | |
| BRAF mutation status ³ | X | | | | | | | | | | | | | | | | | | | |
| Laboratory Studies | | | | | | | | | | | | | | | | | | | | |
| LDH | | X | | | | | X | | | X | X | X | X | X | X | X | X | X | X ⁴ | |
| CBC and serum chemistry | X | X | X | X | X | X | X | | | X | | X | | X | | X | | X | X | |
| Urinalysis | | X | X | X | X | X | X | | | X | | X | | X | | X | | X | X | |
| Pregnancy test | | | | | | | | | | | | | | | | | | | X | |
| Serum FSH/estradiol | | | | | | | | | | | | | | | | | | | | |
| ECG | | | | | | | | | | | | | | | | | | | X | |
| ANA/ESR | X ⁵ | | | | | | | | | X | | X | | X | | X | | X | | |
| Tumor Assessments | | | | | | | | | | | | | | | | | | | | |
| Recurrence Assessment | X ⁶ | | | | | | | | | X | | X | | X | | X | | X | | |
| Dosing | | | | | | | | | | | | | | | | | | | | |
| Seviprotimut-L | | X | X | X | X | X | X | X | X | X | X | X | X | X | X | X | | | | |
| Other Clinical Assessments | | | | | | | | | | | | | | | | | | | | |
| Survival Follow-up Contact | | | | | | | | | | | | | | | | | | | X | |
| Autoimmune Phenomena ⁷ | X ⁸ | | | | | | | | | X | | X | | X | | X | | | | |
| Adverse Events | | X | X | X | X | X | X | X | X | X | X | X | X | X | X | X | X ⁹ | | | |
| Concomitant Medications | | X | X | X | X | X | X | X | X | X | X | X | X | X | X | X | X | X ¹⁰ | X | |

Note: Visit windows are \pm 3 days for Weeks 2, 4, 6, and 8; and \pm 7 days for subsequent visits.

¹ At time of recurrence or study completion for subjects without recurrence

² If not performed within 30 days prior to planned first dose under Protocol 103A-301OL

³ BRAF tumor mutation V600E status must be either known at Screening or a tumor tissue (fresh or archived sample) must be available for testing during the Study.

⁴ For subjects who have not had recurrent disease

⁵ If not performed within 30 days prior to planned first dose under Protocol 103A-301OL

⁶ If not performed within 30 days prior to planned first dose under Protocol 103A-301OL

⁷ Include eye exam (by an ophthalmologist) and skin exam for vitiligo and rashes thereafter.

⁸ If not performed within 30 days prior to planned first dose under Protocol 103A-301OL

⁹ Adverse events collected through 30 days after last dose.

¹⁰ New cancer treatments only

3.0 STUDY OBJECTIVES AND ENDPOINTS

3.1 Part A Study Objectives

Part A is designed to determine the safety profile and immunogenicity of two different doses of seviprotimut-L – 40 µg or 100 µg vs. placebo – and to determine the dose to be used in Part B. The decision to proceed to Part B will be based on evidence of immunogenicity, safety, and tolerability.

3.2 Open-label Extension of Part A Study Objectives

The open-label extension of Part A is to evaluate the safety of seviprotimut-L 40 µg and assess the efficacy (recurrence-free survival [RFS] and overall survival [OS]) of treatment with seviprotimut-L 40 µg in patients who received placebo in Part A.

3.3 Parts B1 and B2 Study Objectives

Parts B1 and B2 allow an evaluation of efficacy using the 40 µg dose of seviprotimut-L selected from Part A. The objective of the Part B1 efficacy evaluation is to assess whether subjects randomized to the active arm have superior RFS compared to subjects randomized to the placebo arm. The safety of seviprotimut-L will also be assessed. Part B1 has a relaxed type I error probability. Survival in Part B1 will be assessed as a safety outcome at the time of the final Part B1 RFS analysis. Patients enrolled in Part B1 will be followed for survival and have their vital status systematically assessed following the Part B1 RFS analysis in order to descriptively assess survival experience of Part B1 patients. The survival data from Part B1 will not be pooled with survival data from Part B2 for the formal survival analysis of Part B2.

Part B2 objectives include two primary endpoints of RFS and survival, and the statistical design is consistent with being a pivotal trial with the type I error probability shared between the two primary endpoints.

3.4 Part A Study Endpoints

3.4.1 Primary Endpoints

The following endpoints will be evaluated on data collected through Week 10 for subjects enrolled in Part A of the study.

- The biological activity of seviprotimut-L as measured by either:
 - the percentage of subjects who have generated either an IgG or IgM response to antigens contained in the vaccine at Week 10; or
 - the percentage of subjects who have generated a T-cell response (as measured by Elispot assay) to Trp-2 antigen at Week 10.

3.4.2 Safety Endpoints

The safety of seviprotimut-L will be evaluated by safety blood and urine laboratory measurements, physical examinations, and AE reports.

3.5 Open-Label Extension of Part A Study Endpoints

- The safety of seviprotilimut-L evaluated by safety blood and urine laboratory measurements, physical examinations, and AE reports.
- Recurrence-free survival (RFS)
- Overall survival (OS)

3.6 Part B1 Study Endpoints

3.6.1 Primary Endpoint

- Recurrence-free survival (RFS)

3.6.2 Secondary Endpoint

- Survival

3.6.3 Safety Endpoints

The between-arm comparison of safety endpoints for Part B1 of this study are:

- The incidence of all adverse events (AEs) reported during the study, including the seriousness, severity, and assessed relatedness to study drug
- Number and percent of patients discontinued from study drug treatment due to AEs
- Change from baseline in vital signs, laboratory data, and electrocardiograms (ECGs)

3.7 Part B2 Study Endpoints

3.7.1 Primary Endpoints

- Recurrence-free survival (RFS)
- Survival

These two primary endpoints share the overall type I error probability.

3.7.2. Safety Endpoints

The between-arm comparison of safety endpoints for Part B2 of this study are:

- The incidence of all adverse events (AEs) reported during the study, including the seriousness, severity, and assessed relatedness to study drug
- Number and percent of patients discontinued from study drug treatment due to AEs
- Change from baseline in vital signs, laboratory data, and electrocardiograms (ECGs)

3.8. Exploratory Endpoints

The primary endpoints will be explored by the following baseline characteristics: stage of disease (Stage IIB vs. Stage III), gender (female vs. male), age (< 60 vs. \geq 60), ECOG Performance Status (0 vs. 1), presence of ulceration (present vs. absent), site (extremity vs. trunk), lymph node status (sentinel LN only positive vs. other), antibody response (positive vs. negative), Elispot response (positive vs. negative), BRAF tumor mutation status, and clinical site based on region or number of patients enrolled. Other characteristics may be added as the data are evaluated.

Sensitivity analyses will be performed to investigate influences on the outcome of the primary endpoints. The details of these analyses are discussed in Section 6.8.3 “Sensitivity Analyses of Parts B1 and B2 Efficacy Endpoints.” Biomarker assessment will be evaluated. Time to locoregional recurrence and time to distant recurrence will be analyzed.

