6.0 STATISTICAL ANALYSIS

Categorical variables will be summarized using counts and percentages. Percentages are based on the number of patients in the analysis set for whom there are non-missing data, unless otherwise specified.

Continuous variables, including change from baseline, will be summarized using descriptive statistics [n, mean, standard deviation (SD), minimum, median, maximum].

The rates of binary endpoints will be compared using a one-sided Pearson χ^2 test for unstratified analyses and Cochran-Mantel-Haenszel (CMH) test for stratified analyses. For the unstratified analyses, point estimates of the rates for each treatment arm and difference of the rates between treatment arms will be provided along with the corresponding 2-sided 95% confidence intervals using an exact method based on the F distribution and using a normal approximation for constructing a confidence interval for differences, respectively. For the stratified analyses, the relative risk ratio estimator will be used to contrast the treatment effects on the endpoint. Both a point estimate and a 2-sided 95% confidence interval will be calculated using a normal approximation.

Time-to-event endpoints will be summarized using the Kaplan-Meier method and displayed graphically when appropriate. Median event times and 2-sided 95% confidence interval for each median will be provided. Cox proportional hazard models will be used to explore the potential influences of the baseline stratification factor on time-to-event endpoints. The estimated hazard ratio and 2-sided 95% confidence interval will be provided.

Stratified analyses will be conducted controlling for the randomization stratification variables of disease state (IIB/IIC vs. IIIA vs. IIIB/IIIC).

Baseline is defined as the last data point prior to randomization in Part A or Part B of the study, unless otherwise stated. Baseline is defined as the last data point prior to dosing in the open-label extension of Part A, unless otherwise stated.

Patient data listings will include all enrolled or randomized patients as applicable to Part A, open-label extension of Part A, or Part B of the study. Listings will be presented by or include part of the study where appropriate, and be sorted by treatment group, site, patient number, and date (if applicable).

Statistical analyses will be carried out using SAS statistical analysis software version 9.1.3 or higher (SAS Institute, Inc., Cary, North Carolina, USA).

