6.9.3 Sensitivity Analyses of Efficacy Endpoints

6.9.3.1 Sensitivity Analyses of Overall Survival (OS)

The following sensitivity analyses for OS will be performed:

- The primary OS analysis will be performed using the ATAS.
- Deaths that occur after the cutoff will not be censored.
- Clinical site homogeneity will be assessed by testing the arm by site or site class interaction. This open-ended exploration will assess homogeneity across sites using the following clumping of sites: Clinical sites with patients fewer than K patients in either arm will be pooled into a single pseudo clinical site. K will be varied in the range of 2 to 8. Classes of clinical sites will be analyzed according to characteristics such as region, type of facility, or homogeneity of medical practice for treating melanoma.
- The proportional hazard regression (PHR) will be re-run without the strata statement and with the treatment arm by stratum interaction term added to the model statement in order to assess the interaction between the treatment arms and the disease states at randomization.
- Effect modifier analyses will be performed for base attributes and particularly putatively prognostic factors, including those explored previously in the literature as well as those hypothesized to be predictive in the context of this study. These are listed subsequently. Effect modification will be assessed one factor at a time in stratified PHR models. Each factor will be analyzed as either a natural dichotomy, a dichotomized ordered categorical with cutpoint chosen based on biologic considerations, or a continuous variable dichotomized at the overall median, and possibly tertiles, quartiles or quintiles. A separate hazard ratio estimate for arm and its 95% confidence interval will be computed for each level of the categorical attribute

using contrast statements in SAS PROC PHREG. Kaplan-Meier estimates of combinations of arm by factor will be plotted on.

- Proportional hazard regression models with multiple added prognostic covariates will be estimated. The covariates to be added will include those explored previously in the literature as well as those hypothesized to be predictive in the context of this study. Interactions will also be explored for contribution to the model.

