6.9.3.2 Sensitivity Analyses of Recurrence-free Survival (RFS)

The following sensitivity analyses for RFS will be performed:

- The same sensitivity analyses specified for as sensitivity analyses of survival will be done for RFS.
- Sensitivity analyses of alternative coding of the date of recurrences and censoring will be performed. These analyses will follow the suggestions in the FDA Guidance for Industry Clinical Trial Endpoints for the Approval of Cancer Drugs and Biologics, May 2007 ([Appendix 3](#)).

All secondary efficacy analyses and sensitivity analyses will be presented by randomized treatment, based on the ITT analysis set, unless otherwise specified.

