6.9.4 Base Attributes to be Assessed

As specified under sensitivity analyses for RFS and Survival analyses the relationship between outcomes and base attributes are planned to be conducted. These base attributes include but are not limited to:

- Stage of disease (Stage IIB v Stage III)
- Sex (F vs. M), age (< 60 vs. \geq 60)
- ECOG Performance Status (0 vs. 1)
- Presence of ulceration (present vs. absent)
- Site (extremity vs. trunk)
- Lymph node status (sentinel LN only positive vs. other)
- Antibody response (positive vs. negative)
- Elispot response (positive vs. negative)
- BRAF tumor mutation status

- Source of the patient (clinical site or various site classes)

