6.10.2 Exploratory Analyses of Other Time-Dependent Outcomes

Other time-dependent outcomes include serially assessed biomarker status, laboratory assessments, and the use of other anti-cancer interventions. These will be analyzed longitudinally using MMRM methods or as time-to-event as appropriate. In addition, the relationship between these other time-dependent outcomes and the primary outcomes will be analyzed using proportional hazard regression with time-dependent covariates.

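### SAP 3.8 and 6.9.4 list antibody and Elispot response as baseline factors, but both are measured after vaccination, so the exploratory arm hazard ratios within response level are not randomised comparisons

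*SAP*

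**What the plan says.** SAP 3.8 opens its factor list with "The primary endpoints will be explored by the following baseline characteristics", and the list contains "antibody response (positive vs. negative), Elispot response (positive vs. negative" beside stage, sex, age, performance status and ulceration. SAP 6.9.4 repeats it under base attributes, including "Antibody response (positive vs. negative" and, as the next item, Elispot response.

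SAP 6.0 fixes the term: "Baseline is defined as the last data point prior to randomization in Part A or Part B of the study, unless otherwise stated". Neither 3.8, 6.9.4 nor Addendum #1 states anything different for these two items.

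For each base attribute, SAP 6.9.3.1 prescribes: "A separate hazard ratio estimate for arm and its 95% confidence interval will be computed for each level of the categorical attribute". It adds curves: "Kaplan-Meier estimates of combinations of arm by factor will be plotted on". SAP 6.9.3.2 carries this over: "The same sensitivity analyses specified for as sensitivity analyses of survival will be done for RFS".

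SAP 6.10.2 has a separate plan for markers measured after baseline: "Other time-dependent outcomes include serially assessed biomarker status, laboratory assessments, and the use of other anti-cancer interventions". These are related to the primary outcomes by proportional hazards models with time-dependent covariates. It does not name antibody or Elispot response.

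**The concern.** A subgroup hazard ratio is protected by randomisation only if the subgroup is fixed before randomisation. Immune response is not: it is the change the vaccine is meant to cause. Positives on vaccine and positives on placebo may be different kinds of patient, and likewise the negatives. The arm hazard ratio within a level can then differ from 1 when the vaccine does nothing.

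The estimate would appear in the same table or plot as true baseline subgroups, with nothing to tell the reader apart. Protocol 1.3.1.2 already reports a relation between vaccine-induced response and better RFS, so a favourable figure among responders would be easy to over-read, and an unfavourable one could count against the vaccine. At stake is the interpretation of exploratory and sensitivity analyses.

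**Working it through.** **1. Timing, from the text.**
- Protocol 11.2 defines both responses by comparing a pre-vaccination sample with the Week 10 sample. SAP 3.4.1 also places both at Week 10.
- The Part B schedule has no Week 10 visit. Protocol 9.3.2 banks Part B samples at day 0, then Months 3, 6, 12, 18, 24 and 36, and at recurrence.
- SAP 2.1 excludes Part A clinical outcomes from the Part B evaluations, so the factor must come from Part B samples.

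Neither response can be known at randomisation. No planned figure is disputed, so there is none to reproduce.

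**2. RFS events before Month 3.** Inputs are the SAP 5.2.1 control rates per year (0.154, 0.198, 0.409) and empirical stage proportions (30.9%, 30.4%, 38.7%).

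Share = sum of p × (1 − exp(−0.25 × rate)) = 0.0117 + 0.0147 + 0.0376 = 0.064.

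That is about 21 of 325 patients in Part B1 and 51 of 800 in Part B2.

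**3. Arm hazard ratio within level, with no vaccine effect.** Assumption: each patient has a latent u, uniform on (0,1), and a hazard multiplier g^(2u−1). A patient whose response is tied to prognosis responds if u < q, where q is the response rate. Mean multipliers at randomisation are:
- responders: m₊(q) = [g^(2q−1) − 1/g] / (2q ln g)
- non-responders: m₋(q) = [g − g^(2q−1)] / (2(1−q) ln g)
- everyone: m = (g − 1/g) / (2 ln g)

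At q = 0.5 the responder hazard ratio is 1/g, so g = 1.25 and 1.5 mean 0.80 and 0.67.

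*(a) Equal link in both arms, equal rates.* The ratios are m₊(q)/m₊(q) = 1 and m₋(q)/m₋(q) = 1.

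*(b) Equal link, 45% on vaccine and 25% on placebo* (the example rates in Protocol 11.2).
- g = 1.25: positives 0.886/0.846 = 1.05; negatives 1.108/1.062 = 1.04
- g = 1.5: positives 0.805/0.739 = 1.09; negatives 1.210/1.124 = 1.08

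*(c) Link in the vaccine arm only, placebo response random.*
- At 50% response: positives m₊/m = 2/(1+g) = 0.89 or 0.80; negatives m₋/m = 2g/(1+g) = 1.11 or 1.20
- At 45% on vaccine: positives 0.886/1.008 = 0.88 or 0.805/1.028 = 0.78; negatives 1.108/1.008 = 1.10 or 1.210/1.028 = 1.18
- Overall arm hazard ratio: m/m = 1

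**4. Simulation of the specified estimate.** This used the same stage rates and a stage-stratified Cox model, with everyone classified unless stated. Part B1 had 325 patients, 2:1, cut at 126 events. Part B2 had 800 patients, 1:1, cut at 310 events; its one-year accrual ramp is assumed.

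| Assumption (no vaccine effect) | Arm HR, positives | Arm HR, negatives |
|---|---|---|
| Response unrelated to prognosis, or equal link, equal rates | about 1.0 | about 1.0 |
| Equal link, 45%/25% | 1.04–1.12 | 1.04–1.10 |
| Vaccine-arm link, g = 1.25 | 0.88–0.90 | 1.10–1.13 |
| Vaccine-arm link, g = 1.5 | 0.79–0.81 | 1.19–1.21 |

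In the last two rows, two-sided p < 0.05 in positives occurs in about 7–8% and 12–13% of Part B1 trials, and in about 9–10% and 22–24% of Part B2 trials.

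If response is unrelated to prognosis but every event before Month 3 is coded negative, the arm hazard ratio stays at 0.99–1.02 at equal rates. It is 1.07 in negatives at 45%/25%.

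**The case against.** The best defence has four parts.

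- **The lists are exploratory and open-ended.** SAP 6.9.4 says base attributes rather than baseline, and SAP 6.0 allows exceptions. This limits the consequence. It does not remove the contradiction, because 6.9.4 repeats the 3.8 list and no exception is stated.
- **SAP 6.10.2 already holds a suitable method.** That is so, and serial antibody results fit it naturally. But it leaves the two items on the fixed-factor lists, and 6.9.3.1 still applies to them.
- **The specified estimate may hardly move.** Protocol 1.3.1.1 reports similar dichotomous response rates on placebo and both doses in Part A. At equal rates, cases with no link or an equal link give about 1.0. The larger departures need a link in the vaccine arm only, which no section establishes; Protocol 1.3.1.2 speaks only of vaccine-induced response. This objection stands as to size.
- **Reach in Part B is uncertain, above all for Elispot.** Protocol 3.5.2 and 3.5.3 name Western blot only, and no Part B Elispot analysis is scheduled. The Part B positivity rule is not in these two documents and may be in the Endpoint Charter. This stands, and the fix addresses it.

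A reader might also infer that responders will look much better than non-responders purely because they had to stay event-free until sampling. With 50% response, no true difference and every early event coded negative, that contrast is 0.73. But it is not the estimate that 6.9.3.1 specifies; the arm-by-factor curves would only show it visually. The missing-as-negative rule in Protocol 11.2 belongs to the Part A Western blot. In Part B a sample is taken at recurrence, and Protocol 7.2.4 keeps some patients with early recurrence on schedule. The contrast is 0.85–0.86 if half of the early-event patients are classified normally, 0.92 if three quarters are, and 1.00 if all are. So 0.73 is an upper-end side illustration.

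**Conclusion.** The point holds as a labelling error with an analytic consequence. Two post-randomisation variables sit on lists of baseline factors, and the plan computes arm hazard ratios within them as if they were baseline subgroups. That rests on the text alone.

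The size rests on assumed response rates and prognostic links: from none, through 1.04–1.12 against the vaccine, to about 0.8–0.9 in positives with 1.1–1.2 in negatives. The direction is not fixed.

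Three stronger readings are not supported:
- **That the efficacy conclusions are affected.** The primary RFS and OS tests, alpha and event counts do not use these factors.
- **That a better method would make the within-level comparison causal.** Under the vaccine-arm-only link, a Month 3 landmark still gives 0.88–0.92 or 0.79–0.82 in positives. A time-dependent covariate does not restore randomisation either.
- **That the size for final OS can be stated.** The documents give no OS rates. A constant death rate matched to 157 deaths at 3.93 years (about 0.101 per year, same accrual assumption) reaches 432 deaths at about 9.5 years, not the 13 years in SAP 5.2.2. I therefore give no OS figure.

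The change should be made because the label is wrong and correcting it is easy. The case does not depend on a large effect.

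**What to change.** 1. Remove antibody and Elispot response from the lists in SAP 3.8 and 6.9.4.
2. Name antibody response in SAP 6.10.2 and analyse it there as a time-dependent covariate. If a fixed grouping is wanted, use a Month 3 landmark among patients alive and recurrence-free at that time, with follow-up counted from the landmark.
3. State that patients with an event before the assessment are not coded negative, and give or cite the Part B positivity rule.
4. State whether Elispot response applies to Part B at all.
5. Label every arm comparison within response level as non-randomised, under either method.

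The cost is SAP wording only, with no new visits, samples or alpha. The time-dependent analysis drops no one. The landmark drops up to about 6.4% of patients (about 21 of 325, or 51 of 800) from an exploratory analysis. That is an upper figure, because the first scheduled post-baseline tumour assessment is at Month 6, so some early recurrences would be dated later.
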